| Section 1.3 (Schedule of Activities) | Removed former footnote "d" and revised footnote "k" (previously footnote "l") to remove text that stated a BRV plasma concentration should be taken within 1 day of the occurrence of an SAE. There are no | Error correction; not applicable for this study. |

| Section # and Name | Description of Change | Brief Rationale |
|---------------------------------------|--|---|
| | time approximation points to relate SAEs to BRV plasma concentrations for this study | |
| Section 1.3 (Schedule of Activities) | Edited footnote "d" (previously footnote "e"), which stated no study drug will be dispensed at the FV or EDV to clarify that study drug will only be dispensed at these visits if the study participant is discontinuing study drug and requires down-titration. | Error correction and further clarification of the procedures at the FV or EDV. |
| Section 1.3 (Schedule of Activities) | Removed inclusion of body weight/height and psychiatric/mental status assessments from footnotes "f" and "g" (previously footnotes "g" and "h") describing complete and brief physical and neurological examinations as these assessments are presented as separate line items in Table 1-2. | Body weight, height, and psychiatric/mental status assessments are included in Table 1-2 as separate line items so need not be noted in the descriptions of brief and complete physical/neurological exams. |
| Section 1.3 (Schedule of Activities) | Added EEG assessments to FEV and YEV/EDV/FV to align with the text provided in Section 7.3.1 detailing seizure data based on EEG. | Error correction. |
| Section 1.3 (Schedule of Activities) | Added text to footnote "m" (previously footnote "n") describing assessments conducted for Unscheduled Visits. | Clarification that, in addition to the assessments noted in the Schedule of Activities table, additional assessments can be performed per the Investigator's discretion. |
| Section 2.3 (Benefit/risk assessment) | Added text and supportive publications describing the current approved treatments for absence seizure and their limitations. Text was added to include the risk assessment regarding the potential interaction if concomitant use of BRV and a COVID-19 vaccination were to occur. | Response to Health Authority feedback. Inclusion of the risk assessment for concomitant use of a COVID-19 vaccine and BRV. |
| Section 5.2 (Exclusion criteria) | Added an exclusion criteria for clinically relevant ECG abnormalities. Added a hepatic impairment exclusion criterion, with Child Pugh Score A, B, or C as the basis for determination by the Investigator. Added a new exclusion criterion for participants with known fructose intolerance or hypersensitivity to any of the ingredients in BRV oral solution. | Consistency with parent study, N01269 Response to Health Authority feedback. |

| Section # and Name | Description of Change | Brief Rationale |
|--|--|--|
| | Added a new exclusion criterion for participants with end-stage kidney disease requiring dialysis. | |
| Section 5.3 (Lifestyle restrictions) | Added text to note that concomitant intake of alcohol is prohibited. | Response to Health Authority feedback. |
| Section 6.1.1 (Alternative study treatment supply due to COVID-19) | Removed "depot to participant" as a method for providing IMP to a study participant who is unable to return to the site but wishes to remain in the study. | This method is not permitted due to privacy issues. |
| Section 6.5.2 (Prohibited concomitant treatments [medications and therapies]) | Added text that use of substrates of alcohol dehydrogenase is prohibited. | Response to Health Authority feedback. |
| Section 6.5.3 (Rescue medication) | Revised text to specify that rescue medication includes any treatment with permitted AEDs, including benzodiazepines. | Clarification that benzodiazepines are permitted as rescue medication. |
| Section 7.3.1 (Seizure data based on EEG) | Removed sentence stating the further information on EEG evaluation will be detailed in the EEG manual. | Error correction; there is no manual for locally read EEGs. |
| Section 7.3.2 (Seizure diary) | Added text to clarify that study participants who require down-titration will complete their daily seizure diaries during the Down-titration Period | Clarification of procedures for completion of the seizure diary. |
| Section 8.1.2 (Body weight and height) | Section added for body weight and height, and moved the applicable text from its former location in Section 8.1.1 (Physical examination). | Body weight and height are assessed on a different schedule than for physical examinations; these assessments are presented separately in Table 1-2. |
| Section 8.1.4 (Psychiatric and mental status evaluation) | Section added to provide information regarding the psychiatric and mental status evaluation conducted as a part of each complete neurological examination. | Alignment with the schedule of activities and the CRF. |
| Section 8.1.5 (Vital signs) | Revised text to state that 1 pulse and 1 blood pressure measurement will be recorded instead of an average of 3 consecutive blood pressure measurements. | Alignment with the CRF. |
| Section 8.1.8 (Suicidal risk monitoring) | Revised text to clarify administration of the C-SSRS consistently throughout the protocol. | Consistent presentation of C-SSRS administration. |

| Section # and Name | Description of Change | Brief Rationale |
|--|--|--|
| Section 8.2.5 (Pregnancy), Section 10.4 (Contraceptive guidance and collection of pregnancy information). | Revised text to clarify that a pregnancy will be followed for at least 30 days after the birth of the child and, in certain circumstances, for up to 12 months. | Clarification and consistency of this information across sections of the protocol. |
| Section 8.4 (Treatment of overdose) | Revised text to specify that an overdose should be reported "within 24 hours" instead of "immediately." | Alignment with the 24-hour requirement for reporting of SAEs. |
| Section 8.5 (Pharmacokinetics) | Revised text to specify that drug concentration information that may unblind N01269 will not be reported to investigative sites or blinded personnel until the study has completed (last patient last visit). | Clarification of previously ambiguous text. |
| Section 9.2 (General statistical considerations) | Minor text revisions to refer to all AE outputs and not just AE tables, and remove "blinded" from the description of the data evaluation meeting. | Clarification and error correction. |
| Section 10.1.6 (Source documents) | Provide study-specific details regarding the electronic source document system that will be used for direct data capture. | Clarification and alignment with ICH-GCP. |
| Section 10.2 (Appendix 2: Clinical laboratory tests) | Revised text to specify that laboratory results that could unblind N01269 will not be reported to investigative sites or blinded personnel until the study has been unblinded. | Clarification of previously ambiguous text. |

1 PROTOCOL SUMMARY

1.1 Synopsis

Protocol title: A Multicenter, Open-label, Single-arm Study to Evaluate Long-term Safety, Tolerability, and Efficacy of Brivaracetam in Study Participants 2 to 26 Years of Age with Childhood Absence Epilepsy or Juvenile Absence Epilepsy

Short Title: A long-term safety, tolerability, and efficacy study of brivaracetam in study participants 2 to 26 years of age with childhood absence epilepsy or juvenile absence epilepsy.

Rationale: In a proof of principle study in study participants with photosensitive epilepsy, brivaracetam (BRV) showed dose-dependent efficacy with complete abolition of the evoked generalized photoparoxysmal electroencephalogram (EEG) response after treatment of study participants with an 80mg single dose (Kastelein-Nolst Trenité et al, 2007). The effect compared favorably to the effect seen in a previous study with levetiracetam (LEV) using the same model. Response to treatment in the photosensitivity model may be more indicative of efficacy in generalized epilepsy rather than focal epilepsy (Yuen and Sims, 2014) and both childhood absence epilepsy (CAE) and juvenile absence epilepsy (JAE) are types of generalized epilepsy. Given the limited current treatment options for CAE and JAE, BRV has the potential to be a valuable alternative to the monotherapy treatments currently available for patients with typical absence seizures. An antiepileptic drug (AED) used in monotherapy is preferable as it may improve adherence and tolerability, compared to the use as adjunctive therapy. Brivaracetam treatment is well tolerated and is easy to use without the need for titration.

Objectives and Endpoints

| Objectives | Endpoints/Estimands |
|--|--|
| 
Primary objective
 
To investigate the long-term safety and tolerability of BRV in pediatric study participants with CAE or JAE
 | 
Primary endpoints
 
• Treatment-emergent adverse events 
Estimand
 
1. Population: population as defined in the protocol-specified inclusion/exclusion criteria reflecting the target patient population who receive at least 1 dose of BRV during the study.2. Study participant-level outcome: TEAE occurrence.3. Intercurrent event handling: The intercurrent event of concomitant medication use is handled by using a treatment policy strategy in which all TEAE data are included, regardless of receipt of any concomitant medication. 
The intercurrent event of treatment discontinuation is handled by using a while-on-treatment strategy where observation ends at 14 days after treatment is stopped.
 |

| | |
|---|--|
| | 
4. Population-level summary measure: incidence rates of TEAEs or incidence rates of TEAEs leading to discontinuation.
 |
| To investigate the long-term safety and tolerability of BRV in pediatric study participants with CAE or JAE | 
 Treatment-emergent adverse events leading to discontinuation of study drug 
Estimand
 
 Population: population as defined in the protocol-specified inclusion/exclusion criteria reflecting the target patient population who receive at least 1 dose of BRV during the study. Study participant-level outcome: TEAE leading to discontinuation occurrence. Intercurrent event handling: The intercurrent event of concomitant medication use is handled by using a treatment policy strategy in which all TEAE data are included, regardless of receipt of any concomitant medication. Population-level summary measure: incidence rates of TEAEs or incidence rates of TEAEs leading to discontinuation. |
| Primary objective | Secondary endpoints |
| To investigate the long-term safety and tolerability of BRV in pediatric study participants with CAE or JAE | 
 SAEs Study drug-related TEAEs 
Estimand
 
 Population: population as defined in the protocol-specified inclusion/exclusion criteria reflecting the target patient population who receive at least 1 dose of BRV during the study. Study participant-level outcome: occurrence of events in the list above. Intercurrent event handling: The intercurrent event of concomitant medication use is handled by using a treatment policy strategy in which all TEAE data are included, regardless of receipt of any concomitant medication. 
The intercurrent event of treatment discontinuation is handled by using a while-on-treatment strategy where observation ends at 14 days after treatment is stopped.
 
 Population-level summary measure: incidence rates. |

| Primary objective | Other endpoints |
|---|--|
| To investigate the long-term safety and tolerability of BRV in pediatric study participants with CAE or JAE | 
• TEAEs requiring a change in BRV dose• Maximum intensity TEAE experienced (mild, moderate, and severe)• Drug-related serious TEAEs• Fatal AEs• TEAEs by maximum relationship (related and not related to BRV)• SAEs by maximum relationship (related and not related to BRV) 
Occurrence of other seizure types, including GTCS, based on diary or EEG:
 
• Nonabsence seizures based on 1-hour EEG• Nonabsence seizures based on diary 
Estimand:
 
1. Population: population as defined in the protocol-specified inclusion/exclusion criteria reflecting the target patient population who receive at least 1 dose BRV during the study.2. Study participant-level outcome: occurrence of events in the list of endpoints above.3. Intercurrent event handling: the intercurrent event of concomitant medication use is handled by using a treatment policy strategy in which all TEAE data are included, regardless of receipt of any concomitant medication. 
The intercurrent event of treatment discontinuation is handled by using a while-on-treatment strategy where observation ends at 14 days after treatment is stopped.
 
• Population-level summary measure: incidence rates. |
| To investigate the long-term safety and tolerability of BRV in pediatric study participants with CAE or JAE | 
• Change from Baseline to each applicable visit in safety laboratory tests• Change from Baseline to each applicable visit in ECG parameters• ECG findings at each applicable visit• Physical and neurological examinations findings at each applicable visit |

| | |
|--|---|
| | 
• Psychiatric and mental status at each applicable visit• Changes from Baseline to each applicable visit in vital signs (blood pressure, pulse rate, body temperature)• Changes from Baseline to each applicable visit in body weight and height |
| Secondary objective | Secondary endpoints |
| To investigate long-term efficacy of BRV in pediatric study participants with CAE or JAE | 
• Absence seizure freedom within 4 days prior to or during the 1-hour EEG at each applicable visit 
Estimand:
 
1. Population: the study participant population as defined in the protocol-specified inclusion/exclusion criteria reflecting the target patient population.2. Study participant-level outcome: seizure freedom response while awake on 1-hour EEG at each applicable visit.3. Intercurrent event handling: The intercurrent event of concomitant use of any permitted AED, including benzodiazepines, within 4 days prior to or during the 1-hour EEG is handled in the definition of the participant-level variable implementing a composite strategy in which receiving any permitted concomitant AED, including benzodiazepines, within 4 days prior to or during the 1-hour EEG is counted as nonresponse (ie, considered as having absence seizures during the EEG).4. Population-level summary measure: percentage of study participants free from absence seizures. |
| To investigate long-term efficacy of BRV in pediatric study participants with CAE or JAE | 
• Absence seizure freedom based on diary over the entire evaluation period and by 3-month time intervals 
Estimand
 
1. Population: the study participant population as defined in the protocol-specified inclusion/exclusion criteria reflecting the target patient population.2. Study participant-level outcome: seizure freedom response on diary over the evaluation period and by 3-month time intervals.3. Intercurrent event handling: The intercurrent event of concomitant use of any permitted AED, including benzodiazepines, during each applicable 3-month period is handled in the definition of the participant-level variable implementing a composite strategy in which receiving any |

| | |
|--|---|
| | 
permitted concomitant AED, including benzodiazepines, in the 3-month period or during the visit is counted as nonresponse (ie, considered as having absence seizures).
 
The intercurrent event of diary completion during each applicable period is handled in the definition of the participant-level variable implementing a composite strategy in which completing less than 80% of diaries during the 3-month period is counted as nonresponse (ie, considered as having absence seizures).
 
4. Population-level summary measure: percentage of study participants free from clinical absence seizures.
 |
| Secondary objective | Other endpoints |
| To investigate long-term efficacy of BRV in pediatric study participants with CAE or JAE | 
 Consecutive absence seizure freedom in 6-month periods based on EEG Consecutive absence seizure freedom in 6-month periods based on diary |
| Tertiary/Exploratory | Other endpoints |
| To investigate the long-term effect of BRV on behavior, cognition, and quality of life in pediatric study participants with CAE or JAE | 
 Change from Baseline to each applicable visit in the EpiTrack Junior scores (for study participants 6 to <18 years old) Change from Baseline to each applicable visit in PedsQL Generic Core scale scores from the study participant self-reports (separate questionnaires for participants age in years: 5 to ≤7, 8 to ≤12, 13 to ≤17 years) Change from Baseline to each applicable visit in PedsQL Generic Core scale scores from the parent proxy-reports (separate questionnaires for participants age in years: 2 to ≤4, 5 to ≤7, 8 to ≤12, 13 to ≤17 years) |

AE=adverse event; AED=antiepileptic drug; BRV=brivaracetam; CAE=childhood absence epilepsy; ECG=electrocardiogram; EEG=electroencephalogram; GTCS=generalized tonic-clonic seizure; JAE=juvenile absence epilepsy; PedsQL=Pediatric Quality of Life; SAE=serious adverse event; TEAE=treatment-emergent adverse event

Key inclusion/exclusion criteria

Study participants who previously participated in N01269 and qualify for entry into EP0132 with a confirmed diagnosis of CAE or JAE, and for whom a reasonable benefit from long-term administration of BRV is expected, in the opinion of the Investigator, are eligible to participate. Study participants must not have severe medical, neurological, or psychiatric disorders or laboratory values, which could, at the discretion of the Investigator, affect safe participation in the study or would preclude appropriate study participation. Study participants must also not

have end-stage kidney disease requiring dialysis, hepatic impairment, active suicide ideation, or a lifetime history of suicide attempt.

Overall design

This is a Phase 3, open-label, single-arm, multicenter, long-term follow-up study to evaluate the safety, tolerability, and efficacy of BRV in pediatric study participants with CAE or JAE. The study is designed for study participants in the age range of 2 to 26 years of age, who have participated in study N01269 and qualify for entry into EP0132.

Upon enrollment, eligible study participants will enter the Evaluation Period and start on a BRV dose of 100mg/day (or equivalent dose of 2mg/kg/day for study participants weighing less than 50kg). The dose may be adjusted after 3 days in the range of 50 to 200mg/day (or equivalent dose of 1 to 4mg/kg/day for study participants weighing less than 50kg) based on the individual needs.

The Entry Visit (EV) is the first study visit and is equivalent to last study visit of the core study as defined in the study protocol of N01269. Two weeks (± 2 days) after study start, the study participant will be contacted by phone to check on the appropriateness of the BRV dose. Within each year of study participation during the Evaluation Period, Minimal Evaluation Visits (MEVs) will be performed at Months 3 and 9, Full Evaluation Visits (FEVs) will be performed at Month 6, and Yearly Evaluation Visits (YEVs) will be performed at Month 12. At any time, the study participant may have an Unscheduled Visit if the Investigator or the participant and/or parent(s)/legal representative(s) consider it necessary. For study participants who continue in the study until it ends, the Evaluation Period will last from the EV to the Final Visit (FV). For study participants who prematurely discontinue the study, the Evaluation Period will last from the EV until the Early Discontinuation Visit (EDV).

For study participants who transition to another BRV study or a managed access program or similar type of program or who convert to commercial BRV (if, when, and where available), the FV instead of the EDV will need to be completed; however, down-titration and the Safety Visit (SV) will not be applicable.

For study participants who will discontinue BRV treatment following the EDV or FV, the BRV dose will be reduced by a maximum of half the dose every week for a maximum of 4 weeks until a dose of 1mg/kg/day (50mg/day for study participants with body weight >50 kg) is reached (Down-Titration Period). A Down-Titration Visit (DTV) will be performed at the end of the Down-Titration Period, and study drug will be discontinued at the DTV. After 2 weeks free of study drug (Safety Period), study participants will complete the SV.

Number of Participants

Approximately 140 study participants may enroll in this study, based upon the rollover expectations from N01269 into EP0132.

Treatment Groups and Duration

Brivaracetam (tablet or oral solution) will be administered twice per day in equal doses. Twice daily dosing with equivalent morning and evening doses approximately 12 hours apart is recommended to achieve more regular exposure over the 24-hour interval; however, the dosing amount and schedule may be adjusted as needed to improve tolerability and efficacy in consultation with the Investigator.

Upon enrollment, eligible study participants will enter the Evaluation Period and start on a BRV dose of 100mg/day (or equivalent dose of 2mg/kg/day for study participants weighing less than 50kg). The dose may be adjusted after 3 days in the range of 50 to 200mg/day (or equivalent dose of 1 to 4mg/kg/day for study participants weighing less than 50kg) based on the individual needs. The maximum allowed daily dose in EP0132 is 200mg/day (or equivalent dose of 4mg/kg/day for study participants weighing less than 50kg). Dose adjustments of BRV and/or concomitant AEDs based on clinical judgment are allowed at any time, 3 days after study start and onwards.

The duration of the study per study participant will be 2 years at minimum, until approval of BRV for the indication of CAE or JAE has been obtained for pediatric participants in their age range, until a managed access program is established as allowed per country-specific requirements in addition to legal and regulatory guidelines, or until the investigational product development in the related indication is stopped by the Sponsor, whichever comes first.

This document cannot be used to support any marketing authorization application and any extensions or variations thereof.
PUBLIC COPY

1.2 Schema

Table 1–1: EP0132 schema

| Study Period | Evaluation Period | | | | | | | | Down-Titration Period | Safety Period |
|---------------|--|------------------------------|--|--|--|--------------------------|----------------------|---------------|---------------------------------------|--|
| | EV | TC ^a | MEV | FEV | MEV | YEV | FV | EDV | | |
| Visit Type | EV | TC ^a | MEV | FEV | MEV | YEV | FV | EDV | DTV | SV |
| Visit Timing | Y1, D1 | Y1, D14 | Y1, M3/ Y2, M15 | Y1, M6/ Y2, M18 | Y1, M9/ Y2, M21 | Y1, M12 | Y2, M24 ^c | As needed | | |
| Visit Window | ±7 Days | ±2 Days | ±7 Days | ±7 Days | ±7 Days | ±7 Days | ±7 Days | | | |
| Frequency | | | 3 months after EV and 3 months after YEV for every year of participation | 6 months after EV and 6 months after YEV for every year of participation | 9 months after EV and 9 months after YEV for every year of participation | 12 months after EV | | | | 2 weeks after last dose of study drug |
| BRV Treatment | 100mg/day (2mg/kg/day for participants weighing less than 50kg) | Individual dose ^b | | | | | | | Reduce max dose by ½ until 1mg/kg/day | BRV-free period |
| Duration | ≥2 years ^c | | | | | | | Up to 4 weeks | 2 weeks | |

BRV=brivaracetam; CAE=childhood absence epilepsy; D=Day; DTV=Down-titration Visit; EDV=Early Discontinuation Visit; EV=Entry Visit; FEV=Full Evaluation Visit; FV=Final Visit; JAE=juvenile absence epilepsy; max=maximum; M=month; MEV=Minimal Evaluation Visit; SV=Safety Visit; TC=telephone call; Y=treatment year; YEV=Yearly Evaluation Visit

^a Study participants will be contacted after 2 weeks (±2 days) to check for appropriateness of dose.

^b Participants will receive 100mg/day upon entry into EP0132. The dose may be adjusted after 3 days in the range of 50 to 200mg/day (or equivalent dose of 1 to 4mg/kg/day for study participants weighing less than 50kg) based on the individual needs.

^c The duration of the study per study participant will be 2 years at minimum, until approval of BRV for the indication of CAE or JAE has been obtained for pediatric participants in their age range, until a managed access program is established as allowed per country specific requirements in addition to legal and regulatory guidelines, or until the investigational product development in the related age range of the pediatric population indication is stopped by the Sponsor, whichever comes first.

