4 STUDY DESIGN

4.1 Overall design

This is a Phase 3, open-label, single-arm, multicenter, LTFU study to evaluate the safety, tolerability, and efficacy of BRV in pediatric study participants with CAE or JAE. The study is designed for study participants in the age range of 2 to 26 years of age who have participated in study N01269 and qualify for entry into EP0132.

Upon enrollment, eligible study participants will enter the Evaluation Period and start on a BRV dose of 100mg/day (or equivalent dose of 2mg/kg/day for study participants weighing less than 50kg). The dose may be adjusted after 3 days in the range of 50 to 200mg/day (or equivalent dose of 1 to 4mg/kg/day for study participants weighing less than 50kg) based on the individual needs.

The Entry Visit (EV) is the first study visit and is equivalent to last study visit of the core study as defined in the study protocol of N01269. Two weeks (\pm 2 days) after study start, the study participant will be contacted by phone to check on the appropriateness of the BRV dose. Within each year of study participation during the Evaluation Period, Minimal Evaluation Visits (MEVs) will be performed at Months 3 and 9, Full Evaluation Visits (FEVs) will be performed at Month 6, and Yearly Evaluation Visits (YEVs) will be performed at Month 12. At any time, the study participant may have an Unscheduled Visit if the Investigator or the participant and/or parent(s)/legal representative(s) consider it necessary. For study participants who continue in the study until it ends, the Evaluation Period will last from the EV to the Final Visit (FV). For study participants who prematurely discontinue the study, the Evaluation Period will last from the EV until the Early Discontinuation Visit (EDV).

For study participants who transition to another BRV study or a managed access program or similar type of program or who convert to commercial BRV (if, when, and where available), the FV instead of the EDV will need to be completed; however, down-titration and the Safety Visit (SV) will not be applicable.

For study participants who will discontinue BRV treatment following the EDV or FV, the BRV dose will be reduced by a maximum of half the dose every week for a maximum of 4 weeks until a dose of 1mg/kg/day (50mg/day for study participants with body weight >50 kg) is reached

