(Down-Titration Period). A Down-Titration Visit (DTV) will be performed at the end of the Down-Titration Period, and study drug will be discontinued at the DTV. After 2 weeks free of study drug (Safety Period), study participants will complete the SV.

Brivaracetam (tablet and oral solution) will be administered twice per day in equal doses. The maximum allowed daily dose in EP0132 is 200mg/day (4mg/kg/day). Dose adjustments of BRV and/or concomitant AEDs based on clinical judgment are allowed at any time, 3 days after study start and onwards.

The duration of the study per study participant will be 2 years at minimum, until approval of BRV for the indication of CAE or JAE has been obtained for pediatric participants in their age range, until a managed access program is established as allowed per country-specific requirements in addition to legal and regulatory guidelines, or until the investigational product development in the related indication is stopped by the Sponsor, whichever comes first.

This study will be conducted using a site-based model; all study assessments will be conducted at the study site.

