6.6 Dose modification

Study participants will start on a BRV dose of 100mg/day (or equivalent dose of 2mg/kg/day for study participants weighing less than 50kg). The dose may be adjusted after 3 days in the range of 50 to 200mg/day (or equivalent dose of 1 to 4mg/kg/day for study participants weighing less than 50kg) based on the individual needs.

For study participants who will discontinue BRV treatment following the EDV or FV, the BRV dose will be reduced by a maximum of half the dose every week for a maximum of 4 weeks until a dose of 1mg/kg/day (50mg/day for study participants with body weight >50kg) is reached (Down-Titration Period). A DTV will be performed at the end of the Down-Titration Period, and study drug will be discontinued at the DTV. After 2 weeks free of study drug (Safety Period), study participants will complete the SV.

For study participants who transition to another BRV study or a managed access program or similar type of program or who convert to commercial BRV (if, when, and where available), the FV instead of the EDV will need to be completed; however, down-titration and the SV will not be applicable.

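### Protocol Table 1-1 states the entry dose (footnote b) and the taper end without the body-weight conditions given elsewhere, so a participant could be dosed differently if the schema were used alone

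*Protocol*

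**What the plan says.** **Starting dose.** Footnote b to Table 1-1 reads "Participants will receive 100mg/day upon entry into EP0132". The Entry Visit cell in the treatment row of the same table reads "100mg/day (2mg/kg/day for participants weighing less than 50kg". Section 4.1 has participants "start on a BRV dose of 100mg/day (or equivalent dose of 2mg/kg/day for study participants weighing less than 50kg", and the synopsis and Sections 4.2, 6.3 and 6.6 state the same rule. The sentence of footnote b that follows keeps the under-50-kg condition for the later adjustment range (1 to 4 mg/kg/day).

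**End of the taper.** The down-titration cell of Table 1-1 reads "Reduce max dose by ½ until 1mg/kg/day". Section 6.6 adds a condition for heavier participants, "50mg/day for study participants with body weight >50kg) is reached", and so do the synopsis, Section 4.1 and SAP 2.3.1.

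**Maximum dose.** Section 4.1 says "The maximum allowed daily dose in EP0132 is 200mg/day (4mg/kg/day", and the parenthesis closes there. The synopsis says "The maximum allowed daily dose in EP0132 is 200mg/day (or equivalent dose of 4mg/kg/day for study participants weighing less than 50kg", and Section 6.1 attaches the same condition.

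**The concern.** The study admits participants from 2 to 26 years of age, so weights well below and well above 50 kg are to be expected. The fixed and the weight-based forms of each dose coincide only at 50 kg. A statement that drops the weight condition therefore gives a different number for almost everyone on the affected side of that weight.

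Two things make this more than a typographical matter. First, these are operative dosing statements. The schema is the page that a site is likely to use as a quick reference, and footnote b contradicts a cell of its own table. Protocol 8.4 also defines overdose relative to the dose that the protocol prescribes, so that dose should be unambiguous.

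Second, the starting dose is an analysis input. The SAP version history (entry on Section 10.1) records that it is not captured in the eCRF and has to be assumed from the protocol. The modal-dose calculation (SAP 3.3.10), the dose at discontinuation (3.13.12) and the dose at AE onset (3.13.13) all assume the weight-scaled start.

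**Working it through.** No sample size, power or error rate is involved. The check compares each statement with and without its weight condition.

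**Inputs from the documents:** entry dose 100 mg/day, or 2 mg/kg/day below 50 kg; taper end 1 mg/kg/day, or 50 mg/day above 50 kg; maximum 200 mg/day, or 4 mg/kg/day below 50 kg.

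**Assumption:** the documents give no weight distribution, so the weights below are illustrative.

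**Agreement at 50 kg:** 2 × 50 = 100, 1 × 50 = 50 and 4 × 50 = 200 mg/day. The two forms match there and diverge elsewhere.

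**1. Entry dose, footnote b against the conditioned text.** Footnote dose per kg = 100 / weight; conditioned dose = 2 × weight; conditioned maximum = 4 × weight.

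| Assumed weight (kg) | Footnote b (mg/day) | Footnote b (mg/kg/day) | Conditioned start (mg/day) | Ratio | Conditioned maximum (mg/day) |
|---|---|---|---|---|---|
| 10 | 100 | 10.0 | 20 | 5.0 | 40 |
| 15 | 100 | 6.7 | 30 | 3.3 | 60 |
| 20 | 100 | 5.0 | 40 | 2.5 | 80 |
| 30 | 100 | 3.3 | 60 | 1.7 | 120 |
| 40 | 100 | 2.5 | 80 | 1.25 | 160 |
| 49 | 100 | 2.04 | 98 | 1.02 | 196 |

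The footnote dose exceeds the maximum when 100 / weight > 4, that is, below 100 / 4 = 25 kg. Below that weight the footnote also conflicts with its own next sentence, whose range stops at 4 mg/kg/day.

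**2. Taper end, Table 1-1 cell against the conditioned text.** Cell = 1 × weight; conditioned text = 50 mg/day above 50 kg.

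| Assumed weight (kg) | Table 1-1 cell (mg/day) | Conditioned text (mg/day) | Ratio |
|---|---|---|---|
| 60 | 60 | 50 | 1.2 |
| 80 | 80 | 50 | 1.6 |
| 100 | 100 | 50 | 2.0 |

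At or below 50 kg there is no difference.

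**3. Maximum, Section 4.1 against the synopsis and 6.1.** If the mg/kg figure is taken to apply to everyone, 80 kg gives 4 × 80 = 320 against 200 mg/day. If the 200 mg/day figure is taken to apply to everyone, 12 kg gives 200 against 4 × 12 = 48 mg/day. Each result requires ignoring half of the sentence.

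**4. Consequence for the SAP if a site had used footnote b.** At an assumed 15 kg, SAP 3.3.10 would assume 2 mg/kg/day and place those days in the category from 2.0 to below 3.0 mg/kg/day. The dose taken would be 6.7 mg/kg/day, which belongs in the category of 4.0 mg/kg/day or more. The misclassification would last until a later dose record replaced the assumed one.

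**The case against.** The best defence is that these are isolated omissions in a protocol that otherwise states the rules consistently, and much of that defence stands.

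- Marker b is attached to the individual-dose entry in the telephone-call column. The Entry Visit cell, which sets the starting dose, has no footnote and carries the condition. To dose a 15 kg child at 100 mg/day, a site would have to pass over that cell, the rest of the footnote and Section 6.3, where the conditioned dose appears beside the enrolment procedure.
- A reader might infer that Section 4.1 drops all three conditions. It does not: it states the starting and taper-end conditions in full and lacks only the one on the maximum. That sentence can fairly be read as shorthand, because 200 mg/day is in it and the same section gives the adjustment range with its condition.
- The taper cell also omits the weekly step. That is abbreviation, not contradiction; the interval is in the synopsis and Sections 4.1 and 6.6.
- A reader might infer that, say, an 80 kg participant on 75 mg/day is exempt from tapering under Table 1-1 but not under 6.6, so that the SAP's Down-Titration Period becomes ambiguous. The documents do not support this. Neither protocol passage says who is exempt. The exemption is in SAP 2.3.1 and 3.3.2 with the 50 mg/day condition intact, and SAP Table 3-2 identifies down-titration from the eCRF. The SAP rules would be affected only if a site had tapered from the schema cell.

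What the defence does not remove is that the first sentence of footnote b and the taper cell, as they stand, give doses that differ from the rest of the protocol.

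**Conclusion.** The inconsistency is real and confined to three places: the opening sentence of Table 1-1 footnote b, the Table 1-1 down-titration cell and, as a minor point, the maximum-dose sentence in Section 4.1. The footnote matters most. Taken alone it exceeds the stated maximum for any child under 25 kg, a threshold that follows from the protocol's own figures. The sizes at particular weights (6.7 mg/kg/day at 15 kg; a taper end of 80 against 50 mg/day at 80 kg) rest on assumed weights.

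The documents do not show that anyone would be misdosed. Sections 6.1, 6.3 and 6.6 are consistent with one another, so a different dose could arise only if one of the three statements were used alone. The SAP's taper, period and completer rules are unaffected unless a site followed the schema. No endpoint, sample size or other statistical figure changes. The correction should still be made, because these are dosing statements in a study that enrols from 2 years of age and the SAP takes the starting dose from the protocol.

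**What to change.** Reconcile Table 1-1 (footnote b and the down-titration cell) and the Section 4.1 maximum-dose sentence with the synopsis and Sections 4.1, 4.2, 6.1, 6.3 and 6.6, so that the starting dose, the taper end and the maximum each carry the same weight condition wherever they appear. Which dose applies is for the sponsor to confirm; this review takes no position on it. Once the text is settled, check that the starting dose assumed in SAP 3.3.10, 3.13.12 and 3.13.13 and the taper rule in SAP 2.3.1 and 3.3.2 match it. The cost is a change of protocol wording; design, data collection and sample size are untouched.
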